6 STUDY OBJECTIVES

The is a case control study to observe treatment and collect data on two cohorts of patients treated with siltuximab and a corresponding case control group of patients who have developed severe respiratory complications with COVID-19 infection.

Primary objective

Cohort A: reduction of the need of invasive ventilation or 30-day mortality

Cohort B: reduction of mortality

Secondary objectives

Cohort A

Reduction of the need of time of ventilatory support

Improvement of the lung function

Improvement of radiologic findings

Cohort B

Reduction of days of need of intubation

Percentage of patients that undergo to tracheostomy

Improvement of the lung function

Improvement of radiologic findings

Primary endpoint:

Cohort A: Reduction of the rate of need of invasive ventilation or 30-day mortality

Cohort B: Reduction of length of ICU staying or 30-day mortality

Secondary endpoints:

Cohort A

Reduction of days of need of ventilatory support

Improvement of P/F fraction (resolution of ARDS i.e. P/F>300, or increase from baseline value of at least 50% if P/F>100 or 100% if P/F<100, at day 3, 8 and 15)

Reduction of the duration of invasive ventilation or length of ICU

Improvement of radiologic imaging

Cohort B

Reduction of days of need of intubation

Percentage of patients that undergo to tracheostomy

Improvement of P/F fraction (resolution of ARDS i.e. P/F>300, or increase from baseline value of at least 50% if P/F >100 or 100% if P/F<100, at day 3, 8 and 15)

Improvement of radiologic imaging

Exploratory end points

Correlation of outcomes with IL-6 levels

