8 OBSERVATIONAL PLAN

8.1 Overall Study Design and Plan – Description

This is a single-center, observational case control study in Italy that follows the use of treatment siltuximab in patients diagnosed with COVID-19 infection who have developed serious respiratory complications. Retrospective data collection will be carried out on patients who have received the drug through the compassionate use program. (this program is still ongoing, and enrolling patients).

Patients receiving siltuximab will be included into this observational study and will be divided into 2 cohorts, split in an approximate 3:1 ratio: 75% will be in Cohort A and are not in an ICU setting and are not on mechanical ventilation, while 25% will form Cohort B and consists of patients in an ICU setting who are receiving invasive ventilation.

[figure not shown]
Each patient will be matched to a consented case control receiving treatment other than siltuximab for their condition.

Match Criteria

Patients receiving siltuximab and controls will be matched according to the following criteria:

- Age (by decades)
- Sex (M/F)
- P/F fraction (<100, 100-150 or >150) at baseline
- Antiviral therapy

Figure 1: Study Design

Procedures outlined in this protocol are based on the compassionate use program, where patients are managed as per clinicians' best judgement and best practice. No procedures are required by this observational protocol. Data on the procedures already performed during the routine diagnosis and treatment of COVID-19 patients will be collected. The list of clinical and laboratory parameters is provided to direct data collection for this observational study (as available in the medical records).

During their hospitalization, patients will be monitored as per standard hospital practice or as per national (emergency) guidelines in accordance with extraordinary circumstances relating to the COVID-19 outbreak. After discharge, patients will be asked to provide (from their primary health care providers) relevant laboratory results for 30 days following start of COVID-19 treatment via ventilation (either mechanical or non-invasive).

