9 STUDY POPULATIONS

9.1 Eligibility

9.1.1 Inclusion Criteria

Patients must meet the following criteria to be eligible to participate in the study:

- 1. Clinical and radiological diagnosis of pulmonary infection by COVID-19
- 2. Positive microbiological evidence of SARS-CoV-2 infection
- 3. Diagnosis of acute respiratory distress syndrome clinical panel in accordance with Berlin 2012 criteria
- 4. For Cohort A only: subjects are eligible if they are enrolled and treated within 48 hours from the beginning of NIV or CPAP
- 5. For Cohort B only: subjects are eligible if they are enrolled and treated within 48 hours from the beginning of invasive ventilation

While approving this protocol, it is understood that the RA/IEC have approved collection and analysis of the data from deceased patients with COVID-19. See also protocol section 10.1.2.

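### In Cohort A the P/F improvement endpoint is scored whatever support the patient is on, so a patient intubated after NIV or CPAP failure can count as improved while failing the primary endpoint

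*Protocol*

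**What the plan says.** Protocol section 6, repeated in the Synopsis, sets P/F improvement as a Cohort A secondary endpoint and defines it as "resolution of ARDS i.e. P/F>300, or increase from baseline value of at least 50" per cent, with the relative part reading in full "increase from baseline value of at least 50% if P/F>100 or 100% if P/F<100, at day 3, 8 and 15". The thresholds and the days are fixed. The type of support at the reading is not mentioned. Cohort B has the same rule.

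The two cohorts start from different support. Section 8.1 says of Cohort A that "75% will be in Cohort A and are not in an ICU setting and are not on mechanical ventilation", and section 9.1.1 adds for that cohort that "subjects are eligible if they are enrolled and treated within 48 hours from the beginning of NIV or CPAP". Cohort B is already invasively ventilated at entry.

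The Cohort A primary endpoint in section 6 is "Cohort A: Reduction of the rate of need of invasive ventilation or 30-day mortality". Another Cohort A secondary endpoint is "Reduction of the duration of invasive ventilation or length of ICU", so the protocol expects some Cohort A patients to be intubated and keeps following them. Section 10.1.1 lists respiratory parameters, mechanical ventilation and ECMO for 30 days from first ventilation, where available. Sections 11 to 11.2.5 give no rule for P/F values measured after escalation of support.

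**The concern.** In Cohort A the baseline P/F is taken on NIV or CPAP. If the patient fails and is intubated, the day 3, 8 or 15 value is taken under a different and stronger form of support. A rise may then reflect the ventilator rather than recovery of the lung, yet the rule scores it as improvement. Above 300 it is labelled resolution of ARDS. In Cohort B the problem is smaller, because invasive ventilation is already in place at baseline.

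Escalation is left to routine care, "where patients are managed as per clinicians' best judgement and best practice", so intubation may differ between siltuximab patients and matched controls. The group with more NIV or CPAP failures has more patients who can become responders on the ventilator. Section 11 plans a descriptive comparison of the groups on the endpoints, section 8.2 gives direct comparison as a reason for having controls, and section 11.2.5 allows early release of results. A reader could see similar P/F response rates in two groups that differ in how many patients needed intubation.

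**Working it through.** The protocol states no sample size calculation, power or effect size, so there is no figure to reproduce. The check has two parts.

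**1. The rule applied to single patients**

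| Baseline on CPAP | Needed for improvement | Value on ventilator, day 3 | P/F endpoint | Primary endpoint |
|---|---|---|---|---|
| 120 | 1.5 × 120 = 180 | 180 | improved (+50%) | failure (intubated day 2) |
| 90 | 2 × 90 = 180 | 185 | improved (185/90 = 2.06, +106%) | failure (intubated day 2) |

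These values are invented to test the rule. Nothing in sections 6 or 11 prevents the double classification.

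**2. Effect on the group comparison at one assessment day**

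From the documents: up to 50 patients, half on siltuximab, 75% of those in Cohort A. So 50 × 0.5 = 25 and 25 × 0.75 = 18.75, about 19 per group.

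Assumed, because the documents give no such figures:
- responders who are not intubated: 8 of 19 on siltuximab, 5 of 19 on control;
- patients intubated and still ventilated on that day: 5 on siltuximab, 9 on control;
- q, the share of intubated patients who meet the P/F rule on the ventilator, the same in both groups.

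Difference as written = [(8 + 5q) − (5 + 9q)]/19 = (3 − 4q)/19.

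| q | Difference, siltuximab minus control |
|---|---|
| 0 | 3/19 = 15.8 points |
| 0.2 | 2.2/19 = 11.6 points |
| 0.5 | 1/19 = 5.3 points |
| 0.75 | 0 |

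The sign changes only when 4q exceeds 3, that is, q above 0.75. If ventilated patients count as not improved, the difference is 3/19 = 15.8 points whatever q is.

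**Effect on a single group's rate.** Let i be the share intubated and r the share of non-intubated patients who respond. The rate as written is (1 − i)r + iq; with ventilated patients scored as not improved it is (1 − i)r. The gap is iq. For i from 0.2 to 0.6 and q from 0.2 to 0.5, it runs from 0.2 × 0.2 = 4 points to 0.6 × 0.5 = 30 points, or 0.8 to 5.7 of 19 patients.

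**The case against.** **An SAP may deal with it.** Handling of values after escalation is often left to an SAP, and one may exist. But the protocol itself says who is a responder, at which thresholds and on which days. The rule can be applied as it stands, and then gives this result.

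**Two endpoints may disagree.** P/F under any support is a legitimate, if limited, description of lung function, and the need for ventilation is captured by other Cohort A endpoints. This stands: disagreement between endpoints is not in itself an error. The weakness is that the words improvement and resolution of ARDS are applied to values whose change from baseline is mixed with a change of support.

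**The consequence is limited.** This also stands. The endpoint is secondary, section 11.2.3 rules out statistical comparison between the groups, section 8.2 describes the study as hypothesis-generating, and by-subject listings will be presented. No error rate or power is affected.

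**Stronger readings that a reader might infer.** One is that a patient put on ECMO is thereby a primary-endpoint failure. The Cohort A primary endpoint does not name ECMO; such a patient fails only through invasive ventilation or death. Another is that the P/F endpoint would reverse a real difference. Under the inputs above that needs more than 75% of intubated patients to meet the rule, and the documents give no support for such a share. They also give no figures on how far ventilation raises P/F.

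**Conclusion.** The concern holds for intubation in Cohort A. The responder rule is fixed without regard to support, and as written it can score a patient who failed NIV or CPAP as improved. The double classification follows from the text alone.

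Its size does not. It rests on assumed response and intubation counts, on an equal q in both groups, and on the intubated patients still being ventilated at the assessment day. On those assumptions a 16-point difference falls to about 12 points at q = 0.2 and about 5 at q = 0.5. The supported conclusion is dilution towards the group with more intubations; reversal is not shown. The harm is to the reading of a descriptive secondary endpoint, and it is worth correcting because the repair is small.

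**What to change.** In the Synopsis and section 6, add to the Cohort A P/F endpoint that a patient who is on invasive ventilation or ECMO on the assessment day, or has died by that day, counts as not improved at that day, and that a patient since extubated is scored on the measured P/F. Scoring by status on the day matters. A rule that failed everyone ever intubated would mark as not improved a patient intubated on day 2, extubated on day 7 and at P/F 350 off support on day 15, against the stated lung-function objective.

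In both cohorts, tabulate P/F at days 3, 8 and 15 by type of support: none or oxygen, NIV or CPAP, invasive ventilation, ECMO.

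Cost: one sentence in two places and one descriptive table. Ventilation, ECMO and respiratory parameters are already on the data list, to be recorded if available. The stated response rate may be lower in both groups, and the endpoint will overlap in part with the primary endpoint. Only scoring changes; no treatment decision is touched.

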5.1 Study Rationale

There is an emergency situation regarding treating patients with COVID-19 and especially those with lung complications and/or acute respiratory distress syndrome (ARDS), which is the main cause of morbidity and mortality in these patients. Siltuximab (SYLVANT) 400 mg is an approved product and dosage for idiopathic Multicentric Castleman Disease (iMCD): it is not indicated for the treatment of COVID-19 infection. However, due to observed clinical (lung dysfunction) and laboratory (high IL-6) presentation in COVID-19 patients, siltuximab (an IL-6 blocker) may potentially benefit patients who developed respiratory complication.

As siltuximab is being used for the first time in this indication, there is a requirement to collect and analyze efficacy and safety data from both the standard of care and siltuximab

treated patients in order to assess risk/benefit as well as the dosing regimen of siltuximab in this patient population. As this is an observational case control study, only available data will be collected and analyzed.

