10.1.1 Tabulated Overview

All available data will be captured from medical records. The following data will be recorded (if available):

Laboratory-confirmed COVID-19 (Positive, validated RT-PCR Assay of nasopharyngeal swabs and ideally serum)

Demographics
Prior medications used

Past Medical History

The following data will be recorded from the time of first ventilation for 30 days (if available):

General Information	
Hospital admission	
ICU admission	
Mobility	
Respiratory parameters	
Use of inotropic medication	
RR/MAP	
Rx (X-Thorax, CT scans)	
Fever/rash/abnormal cardiac function	
Mechanical ventilation	
ECMO	
Infectious Disease Parameters	
Inflammatory markers	
Peripheral edema	
Cytokine panel- Full Cytokine panel workup pre and post treatment (Serum)	
Pre-treatment CRP Levels	
Post-treatment CRP Levels /24h	
Cardiac parameters/Oxygen saturation	
General Disease Parameters	
APACHE II score	
Performance status (ECOG/Karnofsky)	

Laboratory Assessments

Virus titer

IL-6 status Pre-treatment Serum IL-6 levels (ELISA or similar approach, e.g.: Multiplex cytokine array)

Extended blood panel (Hb/Ht), thrombocytes, including PMBC

Coagulation status

History of HIV/HHV-8/Hepatitis/Tuberculosis infections

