11.2.1.2 Descriptive Statistics for Categorical Data

Absolute frequencies and percentages will be presented. For relevant changes from baseline, shift tables may be presented.

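### P/F improvement at days 3, 8 and 15 is not defined for patients who die, and a percentage among measured patients would describe only survivors still being sampled

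*Protocol*

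**What the plan says.** The Synopsis and section 6 list the same secondary endpoint for Cohort A and Cohort B. Its last branch, for patients with a low baseline value, also names the assessment days: "100% if P/F<100, at day 3, 8 and 15". Each branch of the definition needs a P/F value on the day. Neither place says how a patient counts who has died, been weaned or been discharged by then.

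Four other statements bear on which values will exist and how they are summarised:

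- Section 5.1, on the study as a whole: "only available data will be collected and analyzed".
- Section 10.1.1, on respiratory parameters among other items: "The following data will be recorded from the time of first ventilation for 30 days (if available").
- Section 8.1: "No procedures are required by this observational protocol". For the period after discharge it adds: "After discharge, patients will be asked to provide (from their primary health care providers) relevant laboratory results for 30 days". P/F and blood gases are not named there.
- Section 11.2.1.2, on categorical data: "Absolute frequencies and percentages will be presented". The denominator is not stated.

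Death within the window is expected. 30-day mortality is part of the primary endpoint in both cohorts (for example "Cohort A: Reduction of the rate of need of invasive ventilation or 30-day mortality"), and section 9.1.1 provides for data from deceased patients. Section 11 plans a descriptive comparison of the siltuximab and control groups on the endpoints within each cohort. Section 11.2.3 rules out statistical comparisons.

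**The concern.** A patient who died before day 8 or day 15 has no P/F on that day, and one who recovered and left hospital may have none either. If the percentage is taken among patients with a value, the denominator is itself a result of the disease course and can differ between matched groups. Matching on age, sex, baseline P/F and antiviral therapy cannot correct selection that happens after baseline.

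The direction of the distortion matters here. The Introduction hopes that siltuximab lowers mortality and speeds recovery, and these are the two routes by which values go missing. If that hope is right, fewer treated patients leave the denominator as failures and more leave it as successes. Both shifts lower the treated percentage relative to control. P/F is also the only lung-function endpoint with a numerical threshold. With no test planned, the percentages are what readers will compare.

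**Working it through.** **Group sizes (from the protocol).** Up to 50 patients, half treated, gives 25 treated. The 3:1 split gives 25 × 0.75 = 18.75 in Cohort A and 25 × 0.25 = 6.25 in Cohort B, used below as 19 and 6 per group. The protocol gives no figure of its own for this endpoint to reproduce.

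**Three percentages.** Per group of N patients, let D be dead before the day, R alive and off support without a value, M = N − D − R measured, and I improved among the measured.

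- Measured only: I / M
- All patients, measured improvement only: I / N
- All patients, R also counted as improved: (I + R) / N

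**Worked cases.** All counts are assumed, because the documents give no death, discharge or sampling rates. Each pair is siltuximab v control.

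| Case | D | R | I of M | I / M | I / N | (I + R) / N |
|---|---|---|---|---|---|---|
| Deaths only, N = 19 | 2 v 7 | 0 v 0 | 9/17 v 7/12 | 52.9% v 58.3% | 47.4% v 36.8% | 47.4% v 36.8% |
| Recovery only, N = 19 | 4 v 4 | 9 v 3 | 2/6 v 5/12 | 33.3% v 41.7% | 10.5% v 26.3% | 57.9% v 42.1% |
| Both, N = 19 | 2 v 6 | 9 v 3 | 3/8 v 5/10 | 37.5% v 50.0% | 15.8% v 26.3% | 63.2% v 42.1% |
| Cohort B, deaths only, N = 6 | 1 v 3 | 0 v 0 | 3/5 v 2/3 | 60.0% v 66.7% | 50.0% v 33.3% | 50.0% v 33.3% |

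Where only deaths differ, an all-patient denominator with death as not improved is enough to undo the reversal. Where recovery without a value differs, I / N still favours control, and only (I + R) / N shows the recoveries. So the two all-patient figures have to stand side by side.

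**How often, under assumed rates.** Simulation, 200,000 draws, 19 per group. Let d and r be the probabilities of death and of recovery without a value, and p the probability of improvement among the measured. The expected (I + R) / N is r + (1 − d − r)p.

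- Moderate: d 10% v 30%, r 40% v 20%, p 35% v 50%. Expected (I + R) / N: 0.40 + 0.50 × 0.35 = 57.5% v 0.20 + 0.50 × 0.50 = 45.0%. The measured-only figure favours control in 73% of draws, (I + R) / N in 17%.
- Milder: d 15% v 25%, r 30% v 20%, p 45% v 50%. Expected: 0.30 + 0.55 × 0.45 = 54.7% v 0.20 + 0.55 × 0.50 = 47.5%. The shares are 57% and 27%.
- Equal p: d and r as in the moderate case, p 50% in both. Expected: 0.40 + 0.50 × 0.50 = 65% v 0.20 + 0.50 × 0.50 = 45%. The shares are 48% and 8%. The measured-only figure shows no difference.

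**When nothing goes wrong.** If d and r are the same in both groups, all three expected percentages are ordered by p alone and agree in direction. A reversal needs death or recovery to differ between the groups.

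**The case against.** The strongest objection is that the protocol does not prescribe a measured-only analysis of P/F. A reader might infer one from the sentence in section 5.1, but that sentence closes the study rationale and describes the data source: existing records, no added procedures. The wording in section 10.1.1 governs recording. Death and ventilation status are available data too, so an all-patient denominator is compatible with both. It would be equally wrong to say that the protocol as written rewards early death. That follows only if the dead are left out, and no section says so. This objection stands.

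Denominator rules for a secondary endpoint are often left to a statistical analysis plan, and one may exist. That stands as a reason for modest weight. It does not remove the point, because the definition in section 6 itself yields no answer for a patient who has died, in a study with 30-day mortality in both primary endpoints.

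The endpoint is secondary and descriptive, deaths are reported in the primary endpoint, and section 11.2 promises by-subject listings. All true, so deaths would not be hidden. The group percentages would still be set side by side under section 11.

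The examples are built to reverse. They show possibility only. Missing P/F after discharge is an inference: section 8.1 asks for laboratory results, does not name P/F and requires no measurement.

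Finally, being off support does not establish that a P/F threshold was met. That stands, and is why such patients are not counted as improved in the main figure proposed below.

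**Conclusion.** The point holds in a limited form. P/F improvement is defined only by a measured value, no value is required, and no denominator is stated. It is certain that patients who died before the day have no value, and plausible that some weaned or discharged patients have none. A percentage among measured patients is then conditioned on survival and continued sampling, and can mislead in the planned descriptive comparison.

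The size is unknown. Under assumed counts, deaths alone can turn a 10.5-point advantage (47.4 − 36.8 = 10.6 from rounded figures; 2/19 exactly) into a 5.4-point deficit (58.3 − 52.9). A reader might infer that such a reversal is likely. The documents do not support that, because they give no death, discharge or sampling rates and the result depends on these differing between groups. Nor is day 3 shown to be materially affected: fewest patients will have died or left by then, and the concern lies mainly with days 8 and 15. This is worth correcting, but it does not touch the primary endpoints.

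**What to change.** Add to section 11.2.3, for P/F improvement at days 3, 8 and 15:

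1. The denominator is all patients in the cohort and group. Death before the day counts as not improved.
2. At each day, tabulate five states: dead; measured and improved; measured and not improved; alive, off ventilatory support and unmeasured; unknown. Patients alive, still on support and unmeasured belong in the last state, so that the table is complete.
3. In the main figure, only measured improvement counts as improved.
4. A sensitivity figure beside it also counts patients alive, off support and unmeasured as improved.
5. Unknowns are shown as a range: worst case all not improved, best case all improved.
6. The measured-only percentage is kept as supportive, with its denominator printed.

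The cost is a few sentences and one extra table. No new measurement is needed, since survival and ventilation or intubation status are already required for other endpoints. The downside is that the main figure is conservative for patients who recovered without a blood gas. In the recovery-only example it reads 10.5% v 26.3% against 57.9% v 42.1% in the sensitivity figure, so the two should always be reported together with the status table.
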